14.6.2 Extrapyramidal Symptom Rating Scale–Abbreviated (ESRS-A)

The ESRS-A will be assessed at Baseline, at all visits from Week 2 through Week 52, and at unscheduled visits. ESRS-A total scores and the four individual global clinical global impression movement severity scores will be summarized using descriptive statistics at Baseline and each scheduled post-baseline visit. The change from Baseline values will also be summarized at the post-baseline visits.

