#### **4.8.3    Rescue Medications, Treatments, and Procedures**

Rescue medication, as determined by the Investigator, is permitted for a maximum of 7 consecutive days, provided it is consistent with the prohibitions and restrictions in [Appendix A](#) and [Appendix B](#).

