## 6.4 Safety Assessments

As known potential class side effects of antipsychotics, the following adverse events will be actively monitored, including hyperglycemia, leucopenia/neutropenia/agranulocytosis, orthostatic hypotension/bradycardia/syncope, QTc prolongation, akathisia and other extrapyramidal symptoms, weight gain, and somnolence. Criteria for identifying potentially clinically important laboratory values, ECG values, and vital signs are presented in [Appendix C](#), [Appendix D](#), and [Appendix F](#), respectively; and criteria for identifying additional ECG measurements of potential clinical relevance for Medical Monitoring purposes are presented in [Appendix E](#).

Circumstances may arise (e.g., pandemic, natural disaster, political upheaval, or technical issues) when on-site assessments of safety measures may not be possible. In those cases, assessments may be performed at the subject's place of residence either in person or via video technology or telephone, where possible. If a subject is unable to come to the site for lab draws and the site is unable to travel to the subject's place of residence, the subject may visit a local lab to obtain all safety labs. The Investigator must contact the Medical Monitor for approval with the plan. Sites must keep a log to identify details of all visits that are administered remotely.

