## 16 APPENDICES

### Appendix A Prohibited and Restricted Medicationsa

Subjects taking prohibited medications at study entry will not be eligible for the study.

Subjects who require current treatment with a prohibited medication will be withdrawn from the study.

Subjects who have previously taken a prohibited medication during the study will be withdrawn from the study unless:

- the prohibited medication has been discontinued AND
- withdrawal from the study presents an unacceptable medical risk to the subject

The justification to allow the subject to continue in the trial will be made by the Sponsor/Medical Monitor with medical input from the Investigator, and will be documented. If allowed to remain in the trial, this will be reported as a major protocol deviation and not a waiver.

The table below lists prohibitions and restrictions by medication class, including representative medications within class. A **prohibited** medication is not allowed. A **restricted** medication is allowed only under certain conditions.

Medication Class	Medication a	Prohibition/restrictions
Antiarrhythmic drugs	PROHIBITED 

• ajmaline

• amakalant, semantilide

• amiodarone

• bretylium

• disopyramide

• dofetilide

• dronedarone

• flecainide

• ibutilide

• procainamide

• propafenone

• quinidine

• sotalol, d-sotalol

	Prohibited at antecedent study entry and throughout the treatment period

Medication Class	Medication a	Prohibition/restrictions
Anticholinergics	PROHIBITED 
 
• Centrally acting anticholinergics 
 
◦ biperiden
 
◦ trihexiphenidyl
 
 
 
	Centrally acting anticholinergic medications are prohibited throughout the treatment period.
	RESTRICTED 
 
◦ benztropine
 
◦ oral diphenhydramine
 
	
 
◦ Benztropine (<math>\leq 6</math> mg/day) is allowed for movement disorders
 
◦ Oral diphenhydramine is allowed at <math>\leq 50</math> mg per day for acute extrapyramidal symptoms
 

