11 CONCOMITANT AND POST-TREATMENT MEDICATION

Concomitant medication is defined as any medication with a start date prior to the date of the open-label first dose and continuing after the open-label first dose date or with a start date between the open-label first dose date and open-label last dose date, inclusive. Any medication with a start date after the date of the last dose of open-label study drug will be considered as post-treatment medication. Concomitant and post-treatment medications will be summarized separately.

Medications will be coded using WHO Drug Dictionary 2021 March or newer version. The number and percentage of subjects taking each drug class (ATC Level 3) and medication preferred term will be tabulated for the Safety Analysis Set. Multiple medication usage by a subject in the same category will be counted only once.

Relationship to COVID-19 will be assessed for selected medications as detailed in the GSD and provided in a listing. Additional summaries of relationship to COVID-19 may be provided.

Listings of the concomitant and post-treatment medications will be provided.

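### SAP 14.6.2 summarises ESRS-A by visit only and never counts subjects who worsened, so brief or treated extrapyramidal episodes are attenuated or missed in that table

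*SAP*

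**What the plan says.** **Purpose of the scale.** Protocol 6.3.2 and SAP 5.2.9 use ESRS-A to watch for worsening of extrapyramidal symptoms or signs, at unscheduled as well as scheduled visits. Protocol 6.4 puts "akathisia and other extrapyramidal symptoms, weight gain, and somnolence" among the effects to be actively monitored.

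**Planned summary.** In SAP 14.6.2 the total score and the four global movement severity scores "will be summarized using descriptive statistics at Baseline and each scheduled post-baseline visit"; change from Baseline is summarised in the same way. SAP 5.1 defines the statistics as n, mean, SE, SD, minimum, maximum and median.

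**Which rating is used.** SAP 5.3.3 makes unscheduled ratings eligible for the visit windows. SAP 5.3.4 then keeps the one closest to the target day. Its rule to consider all post-baseline values applies where an analysis calls for extremes, and 14.6.2 does not call for them.

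**Permitted treatment.** In Protocol Appendix A benztropine, under a daily cap, "is allowed for movement disorders", and oral diphenhydramine is allowed at up to 50 "mg per day for acute extrapyramidal symptoms". Neither entry states a duration. Protocol 4.8.3 says: "Rescue medication, as determined by the Investigator, is permitted for a maximum of 7 consecutive days".

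**Drug-use table.** SAP 11 tabulates subjects by drug class and preferred term: "Multiple medication usage by a subject in the same category will be counted only once". Its definition of concomitant medication covers both drugs already ongoing at the first open-label dose and drugs started later.

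**The concern.** A scale used to detect worsening in individual children needs a summary that says how many worsened. The other safety measures have one. Laboratory values get post-baseline extremes, shifts and counts of potentially clinically important values (SAP 14.2.1). Vital signs and weight get such counts (14.3). ECG gets a post-baseline maximum, a worst interpretation and such counts (14.4). C-SSRS, in the section just before ESRS-A, gets the number and percentage of subjects (14.6.1).

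Two features make the by-visit ESRS-A table insensitive in addition to averaging. A rating taken at onset, at an unscheduled visit, is dropped when a scheduled rating lies closer to the target day. And a child whose symptoms are relieved by a permitted drug contributes the relieved score, with nothing in the table to mark it as taken on treatment.

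At stake is how a near-zero mean change is read. Protocol 1.1.3 cites little or no extrapyramidal effect in adults as an advantage over approved antipsychotics. A flat ESRS-A table could be taken as support for this in children while subject-level worsening goes uncounted on the scale.

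**Working it through.** **Plan's own figure.** The only computed figure is the Rule of Three bound in Protocol 9.3 and SAP 3.5: 3/193 = 1.55%, which agrees with the stated 1.6%. It does not bear on ESRS-A, but it supplies N = 193.

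**Window selection.** The OL Week 28 window in SAP Table 2 runs from day 169 to day 224, so it is 224 − 169 + 1 = 56 days wide, with target day 197. Suppose a child is rated at onset on day 180 (unscheduled) and again on day 199 (scheduled). The distances from target are 17 and 2 days. The day-199 rating enters the table; the onset rating appears only in the listing.

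**Dilution of the mean.** Let k subjects rise by d points, with a fraction r of the rise left at the rating used, and no net change in the rest. The shift in mean change is k × d × r / N. The documents give N = 193 and the 0-120 range (SAP 5.2.9); k, d and r are assumptions.

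- Five subjects, 8 points, untreated (r = 1), all rated in the same window: 5 × 8 / 193 = 0.21 points.
- The same five fully relieved (r = 0): 0 points.
- One such subject in a given window: 8 / 193 = 0.04 points.
- Incidence in the five-subject case: 5 / 193 = 2.6%.

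**Range.** Assume about 2%, 5% or 10% of subjects affected, rises of 5 to 10 points, and treatment leaving 0 to 20% of the rise. Intervals are exact (Clopper-Pearson).

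| Affected | Incidence (95% CI) | Mean shift, untreated | Mean shift, treated |
|---|---|---|---|
| 4/193 | 2.1% (0.6 to 5.2) | 0.10 to 0.21 | 0 to 0.04 |
| 10/193 | 5.2% (2.5 to 9.3) | 0.26 to 0.52 | 0 to 0.10 |
| 19/193 | 9.8% (6.0 to 14.9) | 0.49 to 0.98 | 0 to 0.20 |

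For example, 10 × 10 × 0.2 / 193 = 0.10. Among affected subjects the largest rise falls from 5-10 points to 0-2 after treatment. Two things follow. Even untreated, the mean moves by less than 1 point on a 120-point scale, so most of the insensitivity comes from averaging a rare event. Treatment or window selection then removes most of what is left. A worst-value count is unaffected by later relief, provided the episode was rated at some visit; the drug-start component covers treated episodes that were not.

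**The case against.** The strongest reply is that treated cases are the ones most likely to be counted elsewhere. TEAEs are the primary endpoint, and SAP 14.1 tabulates subjects by preferred term, severity and relationship. Protocol 7.4.1 tells sites that newly prescribed medication may signal an adverse event to be recorded on both forms. SAP 11 counts users of each drug. The study is descriptive, and 14.6.2 carries out what Protocol 9.5.2 asks for. All of this stands, and it limits the point to the ESRS-A table.

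It does not remove the point. Syncope and somnolence each have a direct caregiver query and an instruction to report an adverse event (Protocol 6.4.5 and 6.4.6); no similar rule links a rise in ESRS-A to an adverse event. SAP 11 does not separate new starts from ongoing use or summarise by indication. Appendix A leaves topical diphenhydramine unrestricted, so a count by preferred term need not isolate use for extrapyramidal symptoms.

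A reader might infer several stronger claims that the documents do not support:

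- *That ESRS-A is reported only as means.* Median, minimum and maximum are also given, and all assessments are listed. The maximum shows the largest value but not how many subjects worsened.
- *That these drugs may be taken for the whole 52 weeks.* That rests on silence. Diphenhydramine is tied to acute symptoms, and the 7-day rescue limit in Protocol 4.8.3 may or may not apply.
- *That treated movement disorders vanish from the safety results, or that their incidence is nowhere tabulated.* Those reported as adverse events are tabulated, and an episode still present at the selected rating stays in the ESRS-A table.
- *That ratings are many months apart.* Scheduled visits are at Weeks 2, 6, 12, 20, 28, 36, 44 and 52, so planned gaps are at most 8 weeks.

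**Conclusion.** The point holds for the ESRS-A table and not for the study's extrapyramidal safety reporting as a whole. SAP 14.6.2 gives by-visit distributions from one rating per window and no subject-level count of worsening, so brief or successfully treated episodes are attenuated or missed there.

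The sizes are illustrative. The numbers affected, the rise in points and the degree of relief are not in the documents, and the calculation takes all 193 estimated subjects as enrolled and rated. Across the assumed ranges, an incidence of 2.1% to 9.8% corresponds to a mean shift of 0.10 to 0.98 points untreated and 0 to 0.20 treated. Averaging is the main cause; permitted treatment and window selection add to it. This is a worthwhile, inexpensive improvement and not a flaw that undermines the primary safety analysis.

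**What to change.** Add to SAP 14.6.2:

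1. For each of the four movement severity scores, the number and percentage of subjects whose worst post-baseline value, over all scheduled and unscheduled assessments, exceeds Baseline by at least 1 point and by at least 2 points. The denominator is subjects with a Baseline and at least one post-baseline value.
2. The number and percentage of subjects with either such worsening or a post-Baseline start of benztropine, or of oral diphenhydramine recorded for extrapyramidal symptoms, identified from the concomitant-medication record. This assumes that the record holds route and indication, which should be confirmed; the adverse-event therapy field in Protocol 7.2.6 does not name the drug.

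The sponsor should also reconcile Protocol 4.8.3 with Appendix A, so that it is clear whether the 7-day rescue limit covers these two drugs.

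**Cost.** SAP wording and one extra table, with no new assessments and no change in sample size. The downside is that, over repeated ratings without a control arm, the 1-point count will include some rating fluctuation; showing the 2-point count beside it helps the reader judge how much.

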15 CLINICAL PHARMACOKINETIC AND PHARMACODYNAMIC ANALYSES

Not applicable.

16 INTERIM ANALYSIS

No formal interim analyses are planned for this study.

17 DATA MONITORING/REVIEW COMMITTEE

An independent Data and Safety Monitoring Board (DSMB) will review ongoing safety data including data on AEs, SAEs and safety laboratory data. The DSMB will be independent of the Sponsor and the Investigators and will be empowered to recommend stopping the study due to safety concerns. The roles and responsibilities of DSMB members and planned frequency of meetings will be described separately in the DSMB Charter.

18 COMPUTER METHODS

Statistical analyses will be performed using Version 9.4 (or newer) of SAS® on a suitably qualified and validated environment.

Validation and quality control of the tables, listings and figures containing the results of the statistical analyses will follow appropriate standard operating procedures.

19 CHANGES TO ANALYSES SPECIFIED IN PROTOCOL

No changes have been made to the analyses as specified in the protocol.

21 APPENDICES

21.1 Schedule of Events and Assessments

Period	Baseline ^w	Open-label treatment period									Follow-up
		0	2	6	12	20	28	36	44	52	
Visit Week	0	2	6	12	20	28	36	44	52		56
Visit number	1	2	3	4	5	6	7	8	9		10
Visit window (days)		±3	±3	±3	±3	±3	±3	±3	±3		+3
Type of visit ^c	Clinic	Clinic	Clinic	Clinic	Clinic	Clinic	Clinic	Clinic	Clinic	Clinic	Telephone
Informed consent/assent ^d	X										
Inclusion/exclusion criteria	X ^e										
Physical examination and self- or caregiver-reported Tanner staging ^g	X			X		X		X	X		
Vital signs	X	X	X	X	X	X	X	X	X	X	
Height ^s , weight, and BMI	X	X	X	X	X	X	X	X	X	X	
12-lead ECG ^{f, g, m}	X	X	X	X	X	X	X	X	X		
Clinical laboratory tests ^{g, m, r, v, x}	X			X		X		X	X		
Pregnancy test ^{g, h}	X	X	X	X	X	X	X	X	X	X	
Urine toxicology (drug) screen (UDS) ^o	X								X		
ABC ^q	X	X	X	X	X	X	X	X	X		
CGI-S of irritability	X	X	X	X	X	X	X	X	X		
CGI-I of irritability ⁱ	X	X	X	X	X	X	X	X	X		
RBS-R ^q	X			X		X	X	X	X		
VABS-Socialization ^q	X			X		X	X	X	X		

Table continues on next page

Schedule of Events and Assessments (Continued)

Period	Baseline ^w	Open-label treatment period									Follow-up
		0	2	6	12	20	28	36	44	52	
Visit Week	1	2	3	4	5	6	7	8	9	56	Safety follow-up ^b
Visit number	1	2	3	4	5	6	7	8	9	10	
Visit window (days)		±3	±3	±3	±3	±3	±3	±3	±3	+3	
Type of visit ^c	Clinic	Clinic	Clinic	Clinic	Clinic	Clinic	Clinic	Clinic	Clinic	Clinic	Telephone
CGSQ ^q	X		X		X	X	X	X	X		
C-SSRS ^q	X	X	X	X	X	X	X	X	X	X	
ESRS-A ^q	X	X	X	X	X	X	X	X	X	X	
Assessment of concomitant medications ^p	X	X	X	X	X	X	X	X	X	X	X
Assessment of adverse events	X	X	X	X	X	X	X	X	X	X	X
Assessment of syncope occurrence ^t	X	X	X	X	X	X	X	X	X	X	X
Assessment of somnolence occurrence ^u	X	X	X	X	X	X	X	X	X	X	X
Study drug dispensation	X ^j	X	X	X	X	X	X	X		X ^k	
Study drug return and accountability ^l		X	X	X	X	X	X	X	X	X	

Abbreviations: ABC=Aberrant Behavior Checklist; ASR=accurate symptom reporting; BMI=body mass index; CGI-I=Clinical Global Impression–Improvement; CGI-S=Clinical Global Impression–Severity; CGSQ=Caregiver Strain Questionnaire; C-SSRS=Columbia–Suicide Severity Rating Scale; ECG=electrocardiogram; eGFR=estimated glomerular filtration rate; EOT=end of treatment; ESRS-A=Extrapyramidal Symptom Rating Scale–Abbreviated; ET=early termination; LAR=legally acceptable representative; RBS-R= Repetitive Behavior Scale–Revised; UDS=urine toxicology (drug) screen; VABS=Vineland Adaptive Behavior Scales

- ^a At a minimum the safety assessments indicated should be completed at unscheduled visits. Other assessments may be completed at unscheduled visits at the discretion of the Investigator.
- ^b This visit is a safety follow-up telephone call visit for subjects who complete the study or discontinue treatment prematurely from the study. This visit will occur 30(+3) days after the last dose of study drug. The safety follow-up visit will not be done if the subject withdraws consent to participate in all parts of the study.
- ^c Circumstances may arise (e.g., pandemic, natural disaster, political upheaval, or to minimize subject and caregiver burden) when on-site assessments of efficacy and/or safety are not possible. In those cases, assessments may be performed offsite by raters either in person, or via video technology or telephone

where possible. For all visits that are conducted remotely, the Investigator **must** contact the Medical Monitor for approval of the plan. Sites must keep a log to identify details of all visits that are administered remotely. Provided that the subject is physically in the clinic, and accompanied by a relative, all caregiver-rated assessments may be provided remotely.

- d Consent from the subject, parent/LAR, and caregiver (if different from the parent/LAR), for the present study must be obtained for entry into the present study prior to the final procedures being performed at the end of treatment (EOT) visit in the antecedent double-blind study. Data from the EOT/ET visit procedures of the antecedent double-blind study will be carried over as baseline information in the present study, as applicable
- e All assessments must be completed and subject must meet required eligibility criteria before being enrolled.
- f 12-lead ECGs should be performed in sequential triplicate. Electrocardiograms should be performed before blood sampling or at least 30 minutes after blood sampling. The subject must rest in a sitting or supine position for 5 minutes before the ECG is obtained. One repeat set of triplicate ECGs is allowed at Baseline.
- g Mild sedation is allowed exceptionally for ECGs and blood draws during the study (e.g., alprazolam at a pediatric-appropriate dose per age, and the *lowest dose* deemed necessary by the Investigator) just in cases when the subject's agitation/anxiety does not allow a safe and accurate measurement and the Investigator, with agreement from the caregiver, considers it safe and appropriate for the subject.
- h For female subjects of childbearing potential, a urine pregnancy dipstick test will be completed at all scheduled and unscheduled visits. If positive, the result will be confirmed with a serum pregnancy test.
- i Relative to baseline status in the antecedent double-blind study.
- j The subject and their parent/LAR will be provided instructions for the subject's first dose of study drug on the day after the Baseline visit.
- k Study drug may be dispensed to the subject at unscheduled visits if needed.
- l If visit is remote, accountability will be assessed verbally with the caregiver, and verified at the next clinic visit.
- m The involvement of experienced personnel in the conduction of routine procedures such as blood drawing and ECG recording in this population is strongly recommended.
- n The ET visit will not be done if the subject (and/or parent/LAR) withdraws consent to participate in all parts of the study and withdrawal of consent happens before that timepoint.
- o A urine toxicology dipstick should be used in addition to the urine toxicology screen at the Baseline visit (to confirm eligibility).
- p Including coronavirus disease 2019 (COVID-19) vaccination
- q For scales that require caregiver input, the caregiver should be the parent/LAR or designee. A designee should be a family member, adult and responsible, living with or in very frequent contact with the subject participating in the study, who is committed to providing responses for the caregiver-reported scales for the duration of Studies ACP-103-069 and ACP-103-070. Caregivers providing input for the ABC, RBS-R, and CGSQ scales will be trained in accurate symptom reporting (ASR) prior to completing the scales. ASR training should be done at Screening in the antecedent study (Study ACP-103-069) before the caregiver completes any scales, and repeated whenever there is a change in caregiver or if the site feels a caregiver requires retraining.
- r Prolactin results should be blinded to the Investigator and the Sponsor at Baseline. Results will be monitored by an independent Medical Monitor from the Contract Research Organization (CRO).
- s As measured by stadiometer.
- t If the caregiver reports an occurrence of syncope, the investigator should ask the "syncope adverse event questions" in Appendix G.
- u If the caregiver reports an occurrence of somnolence, the investigator should ask the "somnolence adverse event questions" in Appendix H.

- ^v Circumstances may arise (e.g., pandemic, natural disaster, political upheaval, or technical issues) when on-site clinical laboratory tests are not possible. In those cases, clinical laboratory tests may be performed at the subject's place of residence by study staff or at a local laboratory. The Investigator must contact the Medical Monitor for approval with the plan. Sites must keep a log to identify details of all visits that are administered remotely.
- ^w Procedures performed at the EOT visit for Study ACP-103-069 will be carried over as baseline information, if applicable.
- ^x The creatinine value should also be used to calculate estimated glomerular filtration rate (eGFR) according to the bedside Schwartz equation $eGFR=0.413 \times (\text{height}/\text{serum creatinine})$, where height is in cm, and creatinine is in mg/dL. Subjects are excluded if eGFR is <30 ml/min.

[figure not shown]
